10.2 SETTINGS

The study will include approx. 4 sites or more, if required (Table 1). Estimated total number of recruited patients is 66. Based on feasibility assessments, approximately 66 patients are expected to qualify for the study and undergo surgery. All patients who undergo surgery will be included in the analysis. An anticipated dropout rate is 10%. Finally, number of subjects eligible for analysis: sample size is expected to be at least 60. The prospective recruitment of patients, by enrolling patients who have planned surgery and meet enrolment criteria will last for 12 months from the study start. All recruited patients will be followed up to 36 months after the date of the surgery.

Note: in emergency situation that requires acute surgery with TachoSil application, obtaining informed consent and including the patient in the study after surgery may be considered, if legal and ethical requirements are met.

The study population is paediatric patients undergoing a cardiovascular, hepatic or other solid organs surgery and polytrauma with injuries of blood vessels, parenchymal organs, lungs requiring the use of drugs for local haemostasis, tissue sealing when control of bleeding by standard surgical techniques (such as suture, ligature, clips or cautery) appeared to be ineffective or impractical.

PasTel

Data will be collected from the following age groups :

- Infants and toddlers (≥ 28 days - < 2 years) on the day of signing the ICF
- Children (≥ 2 years – < 12 years) on the day of signing the ICF
- Adolescents (≥ 12 years – less than 15 years) on the day of signing the ICF

Patient age analysis will be conducted throughout the study to ensure a proportional number of participants in each of the three age groups (if possible, approx. 33% per group). Ensuring an adequate number of participants in each age group will ensure that data are collected across a broad paediatric population to assess short- and long-term safety evaluation.

Inclusion/Exclusion criteria

The study population covers paediatric patients undergoing a cardiovascular, hepatic or other solid organs surgery, and polytrauma patients with injuries of blood vessels, parenchymal organs, lungs requiring the use of drugs for local haemostasis, tissue sealing when control of bleeding by standard surgical techniques (such as suture, ligature, clips or cautery) appeared to be ineffective or impractical (secondary haemostatic treatment).

Data will be collected from the following age groups:

- Infants and toddlers (≥ 28 days - < 2 years) on the day of signing the ICF
- Children (≥ 2 years – < 12 years) on the day of signing the ICF
- Adolescents (≥ 12 years – less than 15 years) on the day of signing the ICF

Inclusion criteria

The following individuals are eligible to participate:

- Patients aged from ≥ 28 days to < 15 years on the day of signing the ICF.

Important Note: According to legal regulations in Poland, patients who are 18 years of age or older cannot be treated by paediatric surgeons. Therefore, only patients who are under 18 years of age by the end of the observation period will be included in the study.

- Patients who have planned a cardiovascular, hepatic or other solid organs surgery and polytrauma patients with injuries of blood vessels, parenchymal organs, lungs qualified for elective surgery
- Patients planned to have at least one TachoSil matrix applied (intraoperatively) and without the plan of application of any other products for local haemostasis at the place of TachoSil application will be qualified for the study.

Exclusion Criteria

The following individuals are not eligible to participate:

- they have known, recognized earlier congenital disorders of haemostasis such as haemophilia type A,B,C, Marfan syndrome, Rendu-Osler-Weber disease, congenital thrombocytopathies, e.g. Glanzmann's thrombasthenia, von Willebrand disease type 1,2,3, Fanconi's anaemia.

PasTel

- they have experienced severe coagulopathy defined as: INR >2.0, platelet count (PLT)<50 000 / mm³; APTT>60 seconds in the period from 7 days before to the day of surgery.
- they are hypersensitive to the active substance(s) or to any of the product excipients.
- female patients of childbearing potential: they are pregnant or want to become pregnant or those who do not use sufficient methods of contraception such as contraceptive implant, intrauterine coil and oral hormonal contraception.

The patient who, in the investigator's opinion, presents a known risk of being lost to follow-up during the 36-month follow-up period, based on the screening assessment.

The study period will be divided into enrolment phase and follow-up phase. Both study phases can last simultaneously.

Enrolment phase: The duration of this study phase is set to be 12 months, starting from the commencement of the study at each individual site. The center will be able to start recruiting patients after obtaining, accepting and signing all necessary documents to conduct an observational study in accordance with the regulations of Polish law. The Sponsor will communicate the study start date to the sites through email and telephone contact. Patient enrolment will be carried out amongst those scheduled for upcoming surgeries.

Patients who are scheduled to undergo cardiovascular, hepatic, or other solid organ surgeries, as well as polytrauma with injuries to blood vessels, parenchymal organs, or lungs, will be identified by the designated Investigator during their routine visit to the study site. During this visit, the Investigator will discuss the study details with the patient and/or their legal representative and ask for their willingness to participate. If the patient meets the remaining inclusion/exclusion criteria, including the intraoperative application of at least one TachoSil patch, they will be enrolled in the study. It's important to note that the participating sites will use TachoSil as part of their routine clinical practice in the specified indications mentioned above. TachoSil itself is not considered an intervention in the study; its application during surgery is one of the inclusion criteria. The day on which informed consent is obtained will be considered a screening visit.

For all enrolled patients, they will continue following the routine procedures of the study site leading up to the day of surgery and throughout their hospital stay until discharge. The Investigator will perform safety assessments during the perioperative period, which includes the time from the day of surgery until discharge. These assessments will involve monitoring adverse events (AEs), adverse events of special interests (AESIs), vital signs (blood pressure, heart rate, temperature), and the analysis of relevant clinical laboratory variables as part of the routine procedure (morphology, INR, APTT).

Follow-up phase: The study phase is scheduled to last for up to 36 months following the date of surgery for each enrolled patient. There are six planned follow-up visits: one at 1 month (\pm 15 days) after surgery, another at 3 months (\pm 15 days), a third at 6 months (\pm 15 days), and a fourth, fifth and sixth visits at 12, 24 and 36 months (\pm 30 days) post-surgery, respectively. However, to minimize stress for patients and caregivers associated with the study and the surgical intervention itself, the number and frequency of follow-up visits during the observation period can be align with the routine follow-up procedures of the clinical sites.

The follow-up visits can be conducted in person at the study site if such visits are routinely performed, or they can take the form of telephone interviews with the patient and/or patient

PasTel

legal representative conducted by the Investigator. In both cases eCRF should be completed with all collected and required by Protocol data.

Patients have the right to discontinue their participation in the study at any time and for any reason, whether specified or unspecified.

Furthermore, a patient/legal representative (if applicable) may be withdrawn from the study if the Investigator determines that the patient no longer meets any of the inclusion/exclusion criteria.

Lost-to-follow-up (LTFU)

To ensure the smooth progress of the PasTel study, it is crucial to minimize the occurrence of lost-to-follow-up (LTFU). Loss-to-follow-up refers to patients and/or their legal representative who, at some point during the study, cannot be reached for further follow-up procedures, resulting in an unknown status and the inability to collect important long-term information, including adverse events. On the other hand, "dropout" refers to patients who voluntarily withdraw from the study, with their health status known upon departure.

To minimize lost-to-follow-up, the following follow-up process will be implemented: If a study participant (or their legal representative) does not respond to the initial telephone contact, up to two reminder calls will be made. If there is still no response after three phone calls, the participant will be sent an email or certified letter. The overall objective is to keep the loss-to-follow-up rate below 10 %. Based on the Corza Medical experience and Feasibility analysis, it is anticipated that the final LTFU will be approximately 10 %.

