10. RESEARCH METHODS

10.1 STUDY DESIGN

This is a prospective, multicentre, non-interventional, uncontrolled, observational, post-authorization cohort study aimed at investigating the short- and long-term safety of TachoSil application.

The study will enrol patients undergoing cardiovascular, hepatic or other solid organs surgery, as well as those with injuries of blood vessels, parenchymal organs, lungs requiring the use of drugs for local haemostasis, tissue sealing, and suture support in vascular surgery where standard techniques are insufficient and where TachoSil was used as a secondary haemostatic treatment. The cohort will include patients identified by participating investigators (prospective enrolment). Patients who meet specified inclusion/exclusion criteria and their legal representatives will receive comprehensive information about the study orally and in written form, tailored to their understanding. The investigator will obtain their voluntary, personally signed, and dated informed consent before collecting any study-related information.

Short-term safety data, including adverse events (AEs) and adverse events of special interest (AESIs), will be collected prospectively from the time of informed consent signature, during hospital stay, and until hospital discharge. Time to onset (TTO), duration, severity, outcome, treatment and relatedness to TachoSil will be analyzed for reported AEs and AESI.

All enrolled patients will be followed for up to 36 months after surgery to monitor long-term treatment-related events and their clinically significant consequences.

To minimize stress for patients and caregivers associated with the study and the surgical intervention itself, the number and frequency of follow-up visits during the observation period will align with the routine follow-up procedures of the clinical sites.

Primary endpoint:

1. The proportion of subjects experiencing clinically significant local reactions including abscesses, hematoma formation or foreign body granuloma formulation, at the site of TachoSil application from the start of surgery up to 36 months post-surgery, as detected through routine imaging examinations (X-ray, ultrasound, CT, MRI or intraoperative detection or physical examination).

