12. MANAGEMENT AND REPORTING OF ADVERSE EVENTS / ADVERSE REACTIONS

Definitions

An adverse event (AE) is defined as any untoward medical occurrence in a patient administered TachoSil treatment and which did not necessarily have a causal relationship with this treatment.

For this study, reporting of Adverse Events begins when the patient signs the Informed Consent Form to participate in the study.

The following are not recorded as an AE if recorded at Screening:

- A pre-planned procedure, unless the condition for which the procedure was planned had worsened since baseline.

Treatment-emergent AEs (TEAEs) are defined as AEs with an onset after the start of surgery (date and time of elective surgery start).

Complications to pre-planned procedures are recorded as AEs. Furthermore, postoperative nausea, vomiting, or pain that the investigator considered common and expectable postoperative findings, treated or untreated, are not recorded as AEs. Postoperative nausea, vomiting, or pain considered by the investigator as either uncommon, unexpected, or both, are recorded as AEs. Any worsening in severity or frequency of a baseline concomitant illness or any new illness diagnosed during the study conduct are recorded as AEs.

A serious adverse event (SAE) is defined as any untoward medical occurrence that at any dose:

- results in death. Death itself is not an AE but rather the outcome of an AE, which is to be described using medical terminology. When Death is the only reported event, this will be considered as an event.
- is life-threatening. Life-threatening referred to an event in which the patient is at risk of death at the time of the event. It does not refer to an event that hypothetically might have caused death if it had been more severe.
- requires inpatient hospitalization or prolongation of existing hospitalization. Inpatient hospitalization includes an overnight admission, even if the duration of hospitalization is shorter than 24 hours.
- results in persistent or significant disability/incapacity.
- is a congenital anomaly/birth defect.
- is medically important. Medical judgment is exercised in deciding whether an AE is serious in other situations. Important AEs that are not immediately life-threatening or do not result in death or hospitalization but could jeopardize the patient or could require intervention to prevent one of the other outcomes listed in the definition above are considered as serious.

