- Recovering/Resolving: Condition is improving, and patient is expected to recover from the event
- Recovered with sequelae: As a result of the AE, the patient suffered persistent and significant disability/incapacity (e.g., became blind, deaf or paralyzed)
- Not recovered
- Fatal
- Unknown.

Reporting of adverse events

Throughout the conduct of the study, the Principal Investigator and investigators will be responsible for collecting and reporting adverse events to the Sponsor (Corza Medical). They are responsible for the timely identification, documentation, and reporting of all AEs, AESIs and adverse reactions (ARs) observed during the study. The principal investigator will ensure that all investigators are thoroughly trained in these procedures and understand their responsibilities.

The management of the follow-up of AEs and ARs, including reporting to the sponsor, is a critical component of the study. Investigators are required to provide comprehensive follow-up information on each AE and AR, ensuring detailed documentation of the event's evolution, management, and resolution. This information must be communicated to the sponsor promptly as per the reporting timelines outlined in the protocol. All events that met the definition of an AE and will occur in the period from the patient signing the ICF and until the final follow-up visit (at 36 month \pm 30 days) will be recorded. During follow-up phase of the study, at each contact between the study site and the patient (visit or phone), the patient will be asked no leading questions about AEs, e.g., "Have you experienced any problems since our last contact?"

The investigator will record all AEs on the standard AE Form (electronic CRF). The investigator will record only 1 AE per form.

For SAE/s, the SAE Form (electronic CRF or paper SAE Form if eCRF is out of order) will also be completed. The investigator will have to record the diagnosis if available. If no diagnosis is available, the investigator will record each sign and symptom as individual AEs. The investigator will evaluate the seriousness, severity, outcome, and causality of AEs.

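### Emergency cases may be consented after surgery, but the protocol contradicts itself on whether their adverse events are recorded from consent or from surgery, so early events may go unrecorded

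*Protocol*

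**What the plan says.** **Late entry.** The note in Protocol section 10.2, listed in section 6 as new in version 2.2, says that for emergency surgery with TachoSil "obtaining informed consent and including the patient in the study after surgery may be considered, if legal and ethical requirements are met". It sets no time limit for the late consent.

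**Start of recording, consent reading.** Section 10.1 says that short-term safety data, AEs and AESIs included, "will be collected prospectively from the time of informed consent signature, during hospital stay, and until hospital discharge". Section 12 says: "For this study, reporting of Adverse Events begins when the patient signs the Informed Consent Form to participate in the study". It later limits recording to AEs that "will occur in the period from the patient signing the ICF and until the final follow-up visit".

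**Start of recording, surgery reading.** The enrolment-phase text of 10.2 has the investigator assess the safety of all enrolled patients from the day of surgery to discharge. Section 10.3 lists AE and AESI evaluation under Surgery and again at discharge, and has data copied from medical records. The AESI definition in section 12 runs from the start of surgery to discharge.

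**Endpoints.** The primary endpoint and all three secondary endpoints count from the start of surgery (10.1): the AESI endpoint to discharge, the others to 36 months.

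**Eligibility.** The inclusion criteria admit "polytrauma patients with injuries of blood vessels, parenchymal organs, lungs qualified for elective surgery", and the enrolment-phase text recruits among children with surgery already scheduled. Section 12 has: "Treatment-emergent AEs (TEAEs) are defined as AEs with an onset after the start of surgery (date and time of elective surgery start".

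**The concern.** For a child consented before surgery, recording from consent covers the whole endpoint window. For a child consented afterwards, the time from surgery to consent lies inside every endpoint window but outside the recording window that 10.1 and 12 set. Postoperative bleeding, immediate hypersensitivity and early thrombosis, which make up much of the AESI endpoint, can be expected to cluster there.

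There is also a question of who enters. Late inclusion is optional, has no deadline, and is decided when the early course is already visible. The protocol requires no count of eligible emergency cases left out and does not say how a death before consent is handled. Section 10.9 discusses selection bias but not this route, and the checklist in Annex 2 calls selection bias not relevant.

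Both mechanisms push the observed proportion down, which in a safety study is the direction that falsely reassures. An analysis plan cannot repair this, because it cannot recover events that were never entered or cases that were never counted.

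**Working it through.** **1. The windows compared**

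- Consent before surgery: recording starts before the endpoint window, so there is no gap.
- Consent after surgery, rule in 10.1 and 12: recording starts at consent. The gap is the time from surgery to consent, and the endpoints count it.
- Consent after surgery, text in 10.2 (enrolment phase), 10.3 and the AESI definition in 12: recording covers the time from surgery, so there is no gap.

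Two sites could follow different parts of the protocol and record different events for identical children. The AESI and related-AE endpoints are the most exposed. The primary endpoint is less so, because 10.3 also asks at discharge and at each follow-up contact for clinically significant endpoint events.

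**2. Inputs**

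- Postoperative bleeding in TachoSil-treated children (section 8, Table 4): 16/36 = 44.4%. Serious: 5/36 = 13.9%. Both reproduce the printed figures.
- Planned recruitment 66 with 10% dropout: 66 × 0.90 = 59.4, against a stated expectation of at least 60 (10.2). This agrees to within one patient.
- Not in the protocol, so assumed: f, the share of emergency children entering by late consent; q, the share of event-positive late-consented children whose only events precede consent; e, the share of emergency children never enrolled, all taken to have had the event.

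**3. Events not recorded:** recorded proportion = p × (1 − f × q)

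- f = 10%, q = 25%: 44.4% × 0.975 = 43.3%; serious 13.9% × 0.975 = 13.5%.
- f = 20%, q = 50%: 44.4% × 0.90 = 40.0%; serious 12.5%.
- f = 30%, q = 100%: 44.4% × 0.70 = 31.1%; serious 9.7%.

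Among 66 children, 66 × 16/36 = 29.3 would be expected to bleed. The three cases miss 29.3 × 0.025 = 0.7, 29.3 × 0.10 = 2.9 and 29.3 × 0.30 = 8.8 of them.

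**4. Children not entered:** observed proportion = (p − f × e) / (1 − f × e), with f now the emergency share among all eligible children. For serious bleeding at 13.9%:

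- f = 10%, e = 5%: (0.139 − 0.005)/0.995 = 13.5%.
- f = 20%, e = 10%: (0.139 − 0.02)/0.98 = 12.1%.
- f = 30%, e = 20%: (0.139 − 0.06)/0.94 = 8.4%.

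**5. Against sampling error.** At n = 60 and p = 0.444 the approximate 95% half-width is 1.96 × √(0.444 × 0.556/60) = 12.6 percentage points. The shifts in step 3 are 1.1, 4.4 and 13.3 points. Only the extreme case exceeds the half-width.

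**The case against.** The strongest reply is that the protocol never tells sites to discard early events. Records exist from the moment of surgery, 10.3 has them transcribed, and section 12 itself defines AESIs from the start of surgery. A sensible site would therefore abstract the gap. This stands in part. A reader might infer that the early events of late-consented children are lost, but the text supports only that they may be, depending on which statement a site follows.

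Three further readings go too far.

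- *That late consent breaches the 10.1 requirement to obtain consent before collecting study information.* It does not. Transcribing the hospital record after a late signature complies with that sentence. The real conflict in 10.1 is with prospective collection from consent onwards.
- *That children who die or deteriorate early never enter.* No passage excludes a deteriorated child, and legal representatives may consent. Death before consent is not addressed either way. Selective omission is possible, not established.
- *That this is immortal-time bias.* There is no comparator and no person-time is misallocated. It is delayed entry and selection in a single-arm proportion.

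On size, the objection is also fair. Late inclusion is only an option, no emergency share is given, and Table 4 comes from 36 children in hepatic surgery. With few emergencies the effect is small against the sampling error. Sampling error is at least shown by a confidence interval, however, whereas a one-sided loss is not.

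**Conclusion.** The point holds as an internal contradiction with a possible downward bias. The emergency note, recording from consent, and endpoints counted from surgery do not fit together for a late-consented child, and the text pointing to a surgery start leaves the rule undecided. The elective and scheduled wording was not adapted to the note, so it is also unclear whether emergency cases are eligible.

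The illustrated reduction in the bleeding proportion runs from about 1 point (44.4% to 43.3%) to about 13 points (to 31.1%). It rests wholly on assumed f and q and on no record abstraction. The upper figure requires every affected late-consented child to have had events only before consent. Selective non-entry would act in the same direction.

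A reader might conclude that late-consented children should be kept out of the primary set. The documents do not support that: 10.2 and 10.5 commit to analysing every child who undergoes surgery. At an assumed 25% emergency share, 66 × 0.75 = 49.5 would remain, and 49.5 × 0.90 = 44.6 after dropout, against at least 60 expected. Once events from surgery onwards are abstracted, exclusion is not needed for capture.

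**What to change.** Before data collection starts (planned for 3Q 2026):

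1. In 10.1 and in both places in section 12, state that AE and AESI recording starts at the earlier of consent signature and start of surgery. For late consent, events since the start of surgery are abstracted from the hospital record once consent is given.
2. Remove the word elective from the TEAE definition. Reconcile the emergency note with the inclusion criterion and the enrolment-phase text in 10.2, so that it is clear whether emergency cases are eligible.
3. Keep an anonymous count of eligible emergency TachoSil cases that were not enrolled, including deaths before consent, as far as legal requirements allow.
4. Keep all treated children in the main analysis and report the results with and without late-consented children.

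The cost is protocol wording plus minor abstraction and logging work at the sites. The analysed number does not fall.

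### The criteria in 10.2 admit only planned or elective surgery, but a note in 10.2 admits emergency surgery, and adverse-event recording from consent leaves part of those children's perioperative period uncovered

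*Protocol*

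**What the plan says.** **Eligibility and recruitment (Protocol 10.2; criteria repeated in the Abstract).** The second inclusion criterion covers children with planned surgery and "polytrauma patients with injuries of blood vessels, parenchymal organs, lungs qualified for elective surgery". The third covers "Patients planned to have at least one TachoSil matrix applied (intraoperatively"). Recruitment proceeds "by enrolling patients who have planned surgery and meet enrolment criteria will last for 12 months from the study start", and the enrolment-phase paragraph says: "Patient enrolment will be carried out amongst those scheduled for upcoming surgeries".

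**The note (Protocol 10.2 only).** It says that "in emergency situation that requires acute surgery with TachoSil application, obtaining informed consent and including the patient in the study after surgery may be considered", conditional on legal and ethical requirements. The Abstract does not carry it. Section 6 lists the note as new in version 2.2; the only inclusion-criterion change listed with it concerns when age is determined.

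**Adverse events (Protocol 12).** TEAEs are "AEs with an onset after the start of surgery (date and time of elective surgery start"). Separately, "reporting of Adverse Events begins when the patient signs the Informed Consent Form to participate in the study", and the events to be recorded are those that "will occur in the period from the patient signing the ICF and until the final follow-up visit". Section 10.1 likewise collects short-term safety data from consent onwards and places consent before any study data collection.

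**Endpoints (Protocol 10.1).** The primary endpoint and all three secondary endpoints count from the start of surgery, whatever the type of surgery.

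**The concern.** Two sites can handle the same emergency case differently and both cite the Protocol. One refuses the child under the second criterion; the other enrols under the note. Section 10.2 also lets an investigator withdraw a child who no longer meets the criteria, so an enrolled emergency case could later be removed.

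The note works after surgery and leaves inclusion to discretion. By then the intraoperative course and some early complications are known. Nothing requires every emergency case to be approached, so entry into a safety cohort can depend on the outcome that the cohort is meant to measure.

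Recording is the third issue. If consent follows surgery, a recording period that opens at consent misses the interval in which intraoperative and early postoperative events occur. The endpoints count that interval.

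**Working it through.** **1. The plan's own figure.** 66 recruited with 10% dropout gives 66 × (1 − 0.10) = 59.4, against the stated minimum of 60. This reproduces within rounding. The Protocol does not say how many of the 66, if any, are emergency cases.

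**2. Eligibility.** Take a child who has unplanned acute surgery, receives TachoSil, and whose representative consents the next day.

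| Text in 10.2 | Requirement | Does this child meet it? |
|---|---|---|
| Criterion 2 | Surgery planned, or polytrauma qualified for elective surgery | No |
| Criterion 3 | TachoSil use planned | No as worded; arguable from the enrolment paragraph, which speaks of actual application |
| Recruitment sentence | Planned surgery and enrolment criteria met | No |
| Enrolment phase | Scheduled for upcoming surgery | No |
| Note | Acute surgery with TachoSil, consent afterwards | Yes, at discretion |

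The Protocol does not say that the note overrides the criteria.

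**3. TEAE definition.** The main clause sets onset after the start of surgery, which an emergency case has. Section 10.3 collects the date and time of surgery for every patient. Only the bracket, which specifies elective surgery, leaves this child out.

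**4. Recording window.** Let T0 be the start of surgery and Tc the time of consent.
- AESI endpoint window: T0 to discharge.
- Recording window (section 12): Tc to the 36-month visit.
- Planned case: Tc is before T0, so the whole endpoint window is recorded.
- Emergency case under the note: Tc is after T0, so the interval from T0 to Tc is counted by the endpoint but lies outside the recording rule.

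Unrecorded events can only lower the observed proportion.

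**5. Illustration of the direction (assumed inputs).** Let p be the true proportion with the event in all patients, s the emergency share, and f the fraction of emergency children with the event who had it only before consent and in whom it goes unrecorded. Then observed proportion = p × (1 − s × f).

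For p, use postoperative bleeding in the TachoSil group of Protocol Table 4: 16/36 = 44.4%. The values of s and f are assumptions; the documents give neither.

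| s | f = 25% | f = 100% |
|---|---|---|
| 10% | 43.3% | 40.0% |
| 20% | 42.2% | 35.6% |
| 30% | 41.1% | 31.1% |

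For example, with s = 20% and f = 100%: 44.4% × (1 − 0.20) = 35.6%.

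For scale, the 95% half-width at 44.4% is 1.96 × √(0.444 × 0.556 / n), which is 12.6 points at n = 60 and 12.0 points at n = 66.

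**The case against.** The strongest defence is that the note is a deliberate, narrow and conditional exception, and that little downstream depends on it. Several parts of this stand.

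- Section 10.7 analyses every enrolled child given TachoSil at least once. An emergency case, once enrolled, is therefore in the analysis. The ambiguity is about entry.
- No endpoint is defined through TEAEs, and section 10.7 names no TEAE table. The faulty bracket therefore alters no endpoint.
- The enrolment paragraph describes actual intraoperative application as an inclusion criterion, so failure of the third criterion is arguable. Failure of the second is not.
- Data are transcribed from medical records, the surgery form includes AE and AESI evaluation, and 10.2 describes safety assessment from the day of surgery. A careful site might therefore record pre-consent events anyway. But section 12 says otherwise, so this too depends on the site.
- Table 4 comes from two hepatic-surgery studies, and bleeding is only one AESI component. Most of the illustrated shifts are smaller than the sampling half-width. That limits what the illustration can show, although a confidence interval does not allow for systematic under-recording.

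The defence does not remove the conflict between criteria and note. Eligibility is fixed by the protocol and cannot be repaired in a SAP.

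**Conclusion.** The contradiction is real and stands in current text. The criteria and recruitment text admit planned, scheduled or elective surgery; the note admits acute surgery with later consent. Enrolment of these children is therefore site-dependent and discretionary after early outcomes are known. Recording from consent would tend to understate perioperative AESIs in those consented after surgery. The size cannot be fixed from the documents; the range in the illustration rests wholly on assumed values of s and f and on a borrowed 44.4%. The effect of discretionary entry could go in either direction.

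Four stronger readings are not supported.
- A reader might infer that emergency cases have no TEAE start time. The main clause, the endpoint windows and the collected surgery time all supply one; only the bracket is wrong.
- A reader might infer that these children are at higher risk. The documents do not say so.
- A reader might want to state how far emergency cases would raise the AESI proportion. The documents give neither their share nor their relative risk.
- A reader might take acute trauma to be part of the stated population. That text says polytrauma; acute surgery appears only in the note.

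The point should be corrected before enrolment opens.

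**What to change.** Reconcile the passages in one of two ways.

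1. **If emergency cases are to be included:** extend the second and third inclusion criteria and the recruitment text, in 10.2 and the Abstract, to match the note. Require that all eligible emergency cases be approached regardless of outcome, with a log of those approached and those included. State in 10.1 and section 12 that, once consent is given, AEs and AESIs from the start of surgery are captured from the medical records. Record an elective/emergency flag on the surgery form and show endpoint counts by it, as counts only if the emergency group is small.
2. **If they are not to be included:** delete the note.

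In either case, replace the bracket in the TEAE definition with the date and time of the start of the index surgery.

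The cost is amendment wording and, under the first option, a short approach log, one eCRF tick box and one extra table. No more patients are needed and no treatment changes. Data collection is planned to start in 3Q 2026, so the change is cheap now; inconsistent enrolment cannot be undone later.
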